3.4.3.5.1 Methotrexate Levels need to be **drawn at scheduled times**

3.4.4 Glucarpidase Rescue of Methotrexate toxicity and Acute Renal Failure

3.4.4.1 Glucarpidase may be utilized in addition to leucovorin or levoleucovorin for methotrexate toxicity in the setting of renal toxicity and delayed methotrexate clearance.

3.4.4.2 Glucarpidase **may ONLY be administered** with the approval of a medically responsible study investigator.

3.4.4.3 Clinical prerequisites:

3.4.4.3.1 Serum methotrexate concentration of  $>10$  mcmol/L at 24-48 hours after methotrexate infusion,

3.4.4.3.2 Urine output decreases (less than 50% excretion of the input hydration) or a serum creatinine  $>1.5$ -times the upper limit of normal, and

3.4.4.4 Documented increase of serum creatinine during the infusion period.

3.4.4.5 Glucarpidase administration:

3.4.4.5.1 Glucarpidase 50 Units/kg of body weight is administered as a single IV injection over 5 minutes.

- 3.4.4.5.2 **Do not administer leucovorin or levoleucovorin within 2 hours either before or after a dose of glucarpidase** because reduced folates such as leucovorin and levoleucovorin are substrates for degradation by glucarpidase.
- 3.4.4.5.3 For the first 48 hours after glucarpidase, administer leucovorin or levoleucovorin at the same dose and schedule as were given prior to administering glucarpidase. At times >48 hours after glucarpidase, administer leucovorin or levoleucovorin based on measured methotrexate concentrations.
- 3.4.4.5.4 Do not discontinue leucovorin or levoleucovorin based on the determination of a single methotrexate concentration <0.05 mcg/L. Leucovorin or levoleucovorin should be continued until the methotrexate concentration has been maintained <0.05 mcg/L for a minimum of 3 days.
- 3.4.4.5.5 Continue hydration and alkalinization of urine as indicated per protocol, or as directed by a medically responsible study investigator.

### **3.5 CRITERIA FOR DISCONTINUING RITUXIMAB AND HIGH-DOSE METHOTREXATE WITH LEUCOVORIN RESCUE**

- 3.5.1 Completion of therapy
- 3.5.2 Delayed methotrexate clearance due to impaired renal function, requiring glucarpidase
- 3.5.3 Creatinine clearance <60 mL/min based on a 24-hour urine collection that cannot be corrected within 2 weeks
- 3.5.4 Any creatinine clearance <30 mL/min based on 24-hour urine collection.
- 3.5.5 Inability to tolerate required intravenous hydration (minimum 60 hours of intravenous fluid at a rate  $\geq$ 100 mL/hour)
- 3.5.6 Dose delays in excess of 15 days
- 3.5.7 Withdrawal of consent.
- 3.5.8 Inability to administer to HAART or other oncologic therapies.
- 3.5.9 Progressive neurologic symptoms attributed to progressive AR-PCNSL
- 3.5.10 Untreatable concurrent illness
- 3.5.11 Methotrexate with leucovorin rescue may be discontinued, if in the opinion of the PI or LAI, the risk of continued therapy outweighs the potential benefit of continued therapy, or if patient non-adherence interferes with study objectives.
- 3.5.12 Patients who discontinue Rituximab and methotrexate with leucovorin rescue may continue with “Radiation-sparing Best Available Therapy”, including dose-dense Rituximab, if clinically indicated.

### **3.6 “RADIATION-SPARING BEST AVAILABLE THERAPY” FOR PATIENTS NOT ELIGIBLE FOR HIGH-DOSE METHOTREXATE IN THE PHASE II COHORT**

Patients with EBV+ AR-PCNSL that have co-morbidities prohibiting administration of high dose methotrexate will receive HAART combined with dose-dense rituximab unless there is a clinical reason that this should not be used or would not be considered best therapy, such as hypersensitivity to murine proteins.

Dose dense administration of rituximab increases serum concentration, which would be expected to allow for better distribution to the CNS. Patients will receive one 4-week cycle, consisting of a total of 6 doses of rituximab administered on Days 1, 3, 5, 8, 15, and 21.

Patients who are hypersensitive to murine proteins or any component of rituximab, or other clinical contraindications to using the dose-dense rituximab regimen, will receive HAART (See Section 3.6.2). If clinically indicated, additional chemotherapy or radiotherapy may be employed in such patients (See Section 3.6.3).

### 3.6.1 Rituximab

#### 3.6.1.1 Rituximab 375 mg/m^2 IV days 1, 3, 5, 8, 15, and 21

#### 3.6.1.2 Administer the first dose at an initial rate of 50 mg/hr; if hypersensitivity

reactions and/or infusion-related events do not occur, the infusion rate may be increased in increments of 50 mg/hour every 30 minutes to a maximum infusion rate of 400 mg/hour. Subsequently, rituximab infusions may be administered at an initial infusion rate of 100 mg/hour; the rate of infusion may be increased every 30 minutes in increments of 100 mg/hour as tolerated to a maximum infusion rate of 400 mg/hour. Rituximab must be diluted prior to injection (See Section 9.1). No other drugs should be added or administered in the same IV line as rituximab.

#### 3.6.1.3 Administer acetaminophen 650 mg PO 30-60 minutes prior to starting rituximab administration (May be held if a patient is unable to swallow oral medications).

#### 3.6.1.4 Administer diphenhydramine 25 – 50 mg IV 10-30 minutes prior to starting rituximab administration.

#### 3.6.1.5 Consider holding antihypertensive medication during the 12-hour period prior to dosing rituximab, and on the day of administration, especially if systolic blood pressure is <105 mm Hg. If antihypertensive medications are held, patients should continue to have blood pressure monitored at least every 8 hours.

Antihypertensive medication should generally be continued or resumed if systolic blood pressure is >160 mm Hg or diastolic blood pressure is >100 mm Hg

### 3.6.2 Highly Active Antiretroviral Therapy (HAART)

#### 3.6.2.1 Whenever possible, patients should be taking HAART as soon as is feasible

#### 3.6.2.2 HAART interruptions for toxicity and tolerance are allowed

#### 3.6.2.3 Refusal to adhere to HAART is not permitted, as it is considered part of the oncology therapy for this protocol

#### 3.6.2.4 A regimen of highly active anti-retroviral therapy will be initiated as soon as feasible in all patients. Treatment will in general be based on Department of Health and Human Services Antiretroviral Guidelines for Adults and Adolescents found at <http://www.aidsinfo.nih.gov/guidelines/>. Particular events may require treatment suspension, modification and will be considered individually for best medical care. Therapy may be managed by NCI and or

NIAID co-investigators on this protocol or on NIAID protocols. Recommend tenofovir-free regimen to avoid potential nephrotoxicity and potential effect on methotrexate renal excretion.

### 3.6.3 Treatment modification: “Radiation-sparing Best Available Therapy”

#### 3.6.3.1 Chemotherapy

Alternative or additional chemotherapy may be employed in patients who:

- Cannot receive the methotrexate or the dose-intense rituximab regimens
- Have stable disease or partial response as a best response to therapy
- Have disease recurrence after either regimen

Choice of additional chemotherapeutic agents will be individualized, and agents and regimens used in treating PCNSL in immunocompetent hosts. Patients treated with second-line chemotherapy can be followed on study as long as they remain on HAART and are evaluable for long-term neurocognitive outcomes.

#### 3.6.3.2 Whole Brain Radiation Therapy

Following the Guidelines in Section 3.10 patients may also, or as an alternative, receive whole brain radiation therapy if indicated.

As noted in Section 3.12.2, patients treated with radiotherapy can be followed on study as long as they remain on HAART and are evaluable for long-term neurocognitive outcomes.

### 3.6.4 Supportive Care

The following supportive care measures may be individualized to patients' symptoms and laboratory abnormalities:

#### 3.6.4.1 Filgrastim

##### 3.6.4.1.1 Routine use of filgrastim are not routinely required for this therapy

##### 3.6.4.1.2 Indications for use on this study:

- HIV-related neutropenia
  - Includes neutropenia related to antiretroviral therapy, or other HIV-disease-related therapy
- Rituximab related neutropenia
  - Includes delayed onset neutropenia

##### 3.6.4.1.3 Filgrastim dose will be individually titrated according to the clinical scenario.

##### 3.6.4.1.4 Filgrastim 300-480 mcg/day subcutaneously may be used as needed to maintain the absolute neutrophil count $\geq 1000$ cells/mm^3. Filgrastim will not be administered more than once daily. Intravenous administration may be utilized.

#### 3.6.4.2 Steroids, systemically administered

##### 3.6.4.2.1 Doses of steroids up to dexamethasone 4 mg every 6 hours or equivalent may be used for patients with neurologic symptoms attributed to lymphoma

- 3.6.4.2.2 Duration of steroids will be generally not be greater than 5 days, in same cases tapering of steroids will be required
- 3.6.4.2.3 Courses of steroid treatment may be repeated if needed

### **3.7 SECOND-LINE THERAPY**

Second-line chemotherapy AND/OR radiotherapy assessment and treatment may be included as part of the protocol when necessary for best patient care; in such a case, patient can remain on-study if they are evaluable for disease specific and overall survival endpoints. Importantly, such patients will be assessed for long-term neurocognitive outcomes using protocol defined neuropsychometric testing. This will be to assess in an observational manner late term neurotoxicity should the patient survive long enough to manifest this complication. Patients receiving radiation therapy will be evaluated separately in regards to neuropsychometric testing. As noted in section 3.6 and 5.3.6, patients requiring radiotherapy will be considered treatment failures for statistical purposes of the protocol. If patient is unable or unwilling to participate in neuropsychometric testing, patient will remain on study until completion of second-line therapy at NCI or until referral to another facility, whichever is first.

### **3.8 ON STUDY EVALUATION**

#### **3.8.1 Research Specimens**

##### **3.8.1.1 Baseline**

###### **3.8.1.1.1 Cerebrospinal fluid (not necessary to repeat if previously acquired within 21 days before starting therapy)**

- Ig PCR and EBV PCR (Molecular Pathology, [name], 2N116-A)
- Cytopathology
- Flow Cytometry (Room B1B58)
- Quantitative EBV PCR (CC Microbiology)

###### **3.8.1.1.2 Blood (not necessary to repeat if previously acquired within 14 days before starting therapy)**

- Quantitative EBV PCR (CC Microbiology)
- HIV viral load
- T-cell subsets ([name], Leidos Biomedical Research, Inc., Frederick)
- Storage: 1 red top for serum; 1 yellow top for plasma; 1 green top for cells

###### **3.8.1.1.2 Sequence based HLA B for HLA B\*5701 Pharmacogenetic testing. This may be excluded if HLA type has been previously documented.**

##### **3.8.1.3 Every odd-numbered cycle**

###### **3.8.1.3.1 Blood**

- Quantitative EBV PCR (CC Microbiology)
- HIV viral load

- T-cell subsets ([name], Leidos Biomedical Research, Inc., Frederick)
- Storage: 1 red top for serum; 1 yellow top for plasma; 1 green top for cells

### 3.8.1.4 End of therapy (see [Appendix 3](#))

3.8.1.4.1 Blood: days 29 (+/- 7 days) then monthly for 2 months, then every 2 months x3, then every 3 months x 6, then every 6 months x 2, then every 12 months x 2 (for patients co-enrolled in 01-C-0038 and followed clinically beyond year 3). Also obtain at time of lymphoma recurrence in concert with CSF studies outlined in section [3.8.5.4.2](#)

- Quantitative EBV PCR (CC Microbiology)
- HIV viral load
- T-cell subsets ([name], Leidos Biomedical Research, Inc., Frederick)
- Storage: 1 red top for serum; 1 yellow top for plasma; 1 green top for cells

## 3.8.2 Clinical and laboratory assessments

### 3.8.2.1 Baseline assessment prior to treatment (within 72 hours before therapy)

3.8.2.1.1 Physical examination with particular emphasis on neurological examination)

3.8.2.1.2 Folstein Mini Mental Status Exam (MMSE). See [Appendix 1](#).

3.8.2.1.3 Assignment of Neurologic Function Class (see [Appendix 2](#))

3.8.2.1.4 CBC with differential (CBC with differential drawn up to 24 hours prior to starting therapy acceptable for patients receiving filgrastim to manage neutropenia)

3.8.2.1.5 Electrolytes

3.8.2.1.5.1 Serum creatinine

- calculated and/or measured creatinine clearance
- Whenever the calculated creatinine clearance is <100 mL/min, a measured creatinine clearance should be obtained.

3.8.2.1.5.2 Hepatic panel

3.8.2.1.5.3 Mineral panel

3.8.2.1.6 Ophthalmologic examination to assess for ocular involvement by lymphoma

3.8.2.1.7 Viral hepatitis studies (not necessary to repeat previously documented positive studies; results not required prior to treatment):

- Hepatitis A
- anti-HAV IgG
- Hepatitis B
- anti-HBsAg
- HBsAg
- Anti-HB core
- Hepatitis C
- anti-HCV

- 3.8.2.1.8 Serum anti-toxoplasmosis antibody titers (not necessary to repeat if already obtained on NIAID protocol)
- 3.8.2.1.9 Syphilis serology (not necessary to repeat if already available within 6 months prior to study entry)
- 3.8.2.1.10 HIV viral load if not available within 14 days prior to enrollment
- 3.8.2.1.11 T-cell subsets if not available within 14 days prior to enrollment
- 3.8.2.1.12 HIV genotype or Virtual Phenotype® to assess for resistant HIV if not previously done
- 3.8.3 Day 1 each cycle; then monthly for 2 months, then every 2 months x3, then every 3 months x6, then every 6 months x 2, then every 12 months x 2 (for patients co-enrolled in 01-C-0038 and followed clinically beyond year 3).

For “Radiation-Sparing Best Available Care” Cohort, scheduled evaluations on Days 1, 8, 15, 21, 28 then monthly for 2 months, then every 2 months for 3 times, then every 3 months of total of 36 months, then yearly for 2 years (for patients followed clinically beyond year 3).

- 3.8.3.1 Physical examination with documentation of abnormalities
- 3.8.3.2 Particular emphasis on neurological examination
- 3.8.3.3 Assign neurologic function class (see [Appendix 2](#))
- 3.8.3.4 CBC with differential (CBC with differential drawn up to 24 hours prior to starting therapy acceptable for patients receiving filgrastim to manage neutropenia)
- 3.8.3.5 Electrolytes
- 3.8.3.5.1 Serum creatinine
  - calculated and/or measured creatinine clearance
  - Whenever the calculated creatinine clearance is <100 mL/min, a measured creatinine clearance should be obtained.
- 3.8.3.5.2 Hepatic panel
- 3.8.3.5.3 Mineral panel
- 3.8.3.6 During treatment cycles until serum methotrexate level  $\leq 0.05$  mcmol/L:
  - 3.8.3.6.1 Blood specimens for methotrexate levels must be drawn at scheduled times
  - 3.8.3.6.2 Hepatic panel every other day
  - 3.8.3.6.3 CBC with differential daily
  - 3.8.3.6.4 Electrolytes, creatinine, BUN daily
- 3.8.4 Baseline Staging
- 3.8.4.1 MRI: if done within 2 weeks before study entry, repeat only if interval clinical deterioration has occurred
- 3.8.4.2 FDG-PET: not necessary to repeat if previously done within 3 weeks of study entry
- 3.8.5 Restaging
- 3.8.5.1 MRI
  - 3.8.5.1.1 End of cycles 2, 4, 6 and 8, then every 2 months x3, then every 3 months x 6, then every 6 months x 2, then as clinically indicated, or annually up to year 5

(for patients followed clinically beyond year 3). For “Radiation-Sparing Best Available Care” Cohort, Scheduled evaluations on Week 4, Week 8, Week 12, then every 2 months x3, then every 3 months x 5, then every 6 months x 2, then as clinically indicated, or annually up to year 5 (for patients followed clinically beyond year 3).

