### **3.3 DRUG ADMINISTRATION: HIGH-DOSE METHOTREXATE WITH LEUCOVORIN RESCUE AND RITUXIMAB, AND HAART**

- 3.3.1 Review all concomitant medications prior to day 1 of each cycle. Discontinue any drug that may potentially interact with methotrexate elimination.
- 3.3.2 Rituximab
  - 3.3.2.1 Rituximab 375 mg/m^2 IV day 1 of each cycle prior to administration of high-dose methotrexate.
  - 3.3.2.2 Administer the first dose at an initial rate of 50 mg/hr; if hypersensitivity reactions and/or infusion-related events do not occur, the infusion rate may be increased in increments of 50 mg/hour every 30 minutes to a maximum infusion rate of 400 mg/hour. Subsequent rituximab infusions may be administered at an initial infusion rate of 100 mg/hour; the rate of infusion may be increased every 30 minutes in increments of 100 mg/hour as tolerated to a maximum infusion rate of 400 mg/hour. Rituximab must be diluted prior to injection (See Section 9.1). No other drugs should be added or administered in the same IV line as rituximab.
  - 3.3.2.3 Administer acetaminophen 650 mg PO 30-60 minutes prior to starting rituximab administration (May hold if a patient is unable to swallow oral medications).
  - 3.3.2.4 Administer diphenhydramine 25 – 50 mg IV 10- 30 minutes prior to starting rituximab administration.
  - 3.3.2.5 Consider holding antihypertensive medication during the 12-hour period prior to dosing rituximab, and on the day of rituximab administration.
- 3.3.3 Intravenous fluid and urine alkalization
  - 3.3.3.1 On Day 1, 12 – 18 hours before the anticipated start of methotrexate, start IV hydration containing sodium bicarbonate (NaHCO3) to alkalinize a patient's urine to pH  $\geq$ 7.0, but  $\leq$  8.0 at a rate that achieves a urine output  $\geq$ 100 mL/hr (recommended start by 6PM local time on day 1). See Table below for options recommended to initially produce an alkaline urine.
    - 3.3.3.1.1 Order q 6-hour urine pH measurements (e.g., 0000, 0600, 1200, 1800) and strict urine output monitoring to start with initiation of IV hydration. Record urine output hourly until urine output is  $>$  100 cc/hour, then at least every four hours.
    - 3.3.3.1.2 Nursing staff should notify a medically responsible individual (investigator or staff on-call) for urine output  $<$ 100 mL/hour or urine pH  $<$ 7 or  $>$ 8.

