### 3.9.6 Hepatitis B antigenemia

For patients with serologic evidence of chronic persistent/active HBV infection, lamivudine 150 mg PO daily, tenofovir 300 mg PO daily, or other agents with demonstrated anti-HBV activity should be given continually throughout treatment cycles until a medically-responsible investigator advises discontinuation. Since chemotherapy in general and rituximab in particular are associated with HBV reactivation, this should also be considered in patients with anti-HB core-alone positivity.

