**On-Study Evaluations for Best Available Radiation Sparing Therapy (no Methotrexate)**

Cycle/ Visit	H&P	Ophtho Exam	Toxicity Assess	MMSE	Clin. Labs	Cr. Cl.	Serology	MRI	PET	CSF	HIV/ CD4	EBV	Research Blood	Neuro- psych	Adherence
Screen/BL	X	X			X	X	X	X	X	X	X				
Day 1	X		X	X	X	X					X	X			
Day 3	X		X	X	X	X			X						
Day 5	X		X	X	X	X									
Day 8	X		X	X	X	X									
Day 15	X		X	X	X	X									
Day 21	X		X	X	X	X									
CR by MRI			X 												
End Rx	X	X 	X	X	X	X		X	X	X	X	X	X	X	X
Follow-up															
Week 2	X		X	X	X	X									
Week 4	X		X	X	X	X									
Q2 mo x3															
Month 2	X		X	X	X	X									
Month 4	X		X	X	X	X									
Month 6	X		X	X	X	X									
Q3 mo x6															
Month 9	X		X	X	X	X									
Month 12	X		X	X	X	X									
Month 15	X		X	X	X	X									
Month 18	X		X	X	X	X									
Month 21	X		X	X	X	X									
Month 24	X		X	X	X	X									
Q6 mo x 2															
Month 30	X		X	X	X	X									
Month 36	X		X	X	X	X									
Q12 mo x2															
Month 48	X		X	X	X	X									
Month 60	X		X	X	X	X									

 Repeat if abnormal at baseline.

H&P= History and Physical, including ECOG; Ophtho Exam = Ophthalmology exam for orbital involvement; Clin. Labs = CBC with differential and Retic, Chem. 20, PT/PTT, Urine: UA,  $\beta$ -hCG (women); Cr. Cl. = estimated creatinine clearance by Cockcroft-Gault formula (Appendix 4); Serology = Hepatitis and Toxoplasmosis serologies, RPR; CSF = CSF cell count, glucose, protein, EBV, molecular pathology, flow cytometry; HIV/CD4 = Baseline HIV Serology, genotype if indicated, HIV viral load, and lymphocyte subset TBNK; EBV = EBV quantitative PCR, blood; Neuropsych, See Appendix 5; Adherence, see Appendix 6. BL = Baseline Studies; End Rx = End of therapy, Day 28 (Week 1 follow-up.)

For patients that relapse, re-staging will include: MRI-brain with contrast, CNS FDG-PET, CSF studies, quantitative EBV-PCR, and ophthalmologic examination.

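### Section 3.8.2.1.7 lets rituximab start before HBsAg and anti-HB core results are known, although section 3.9.6 hangs anti-HBV cover during treatment on those results

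*Combined protocol and SAP*

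**What the plan says.** - **Testing (3.8.2.1.7).** Hepatitis A, B and C serology, including HBsAg and anti-HB core, belongs to the "Baseline assessment prior to treatment (within 72 hours before therapy"). The note on these tests reads "not necessary to repeat previously documented positive studies; results not required prior to treatment".
- **Cover (3.9.6).** For patients with serologic evidence of chronic persistent or active HBV, lamivudine, tenofovir or another agent active against HBV "should be given continually throughout treatment cycles until a medically-responsible investigator advises discontinuation". If anti-HB core alone is positive, cover is to be considered. The reason given is that "chemotherapy in general and rituximab in particular are associated with HBV reactivation".
- **Rituximab, main cohort (3.3.2.1).** It is given "IV day 1 of each cycle prior to administration of high-dose methotrexate". Cycles are two weeks apart, and rituximab is given in the first six.
- **Rituximab, no-methotrexate cohort (3.6).** One four-week cycle, "consisting of a total of 6 doses of rituximab administered on Days 1, 3, 5, 8, 15, and 21". This is the default "unless there is a clinical reason that this should not be used or would not be considered best therapy".
- **Schedule (Appendix 3, no-methotrexate table).** The Serology column is marked in the screening/baseline row, and the legend reads "Serology = Hepatitis and Toxoplasmosis serologies, RPR".
- **HAART (3.3.6, 3.6.2, Appendix 9).** HAART starts as soon as feasible, may be interrupted for toxicity or tolerance, and should preferably avoid tenofovir.

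**The concern.** Section 3.9.6 identifies a hazard specific to one of the study drugs and prescribes cover for it. Whether a patient gets that cover depends on serology. Section 3.8.2.1.7 expressly allows that serology to be unknown when the drug is first given. No section holds rituximab until the result returns, and none provides cover in the meantime.

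The stake is patient safety in a small group: patients whose HBV status is undocumented at entry and whose HAART contains no HBV-active drug at dose 1. Within that group, only those who turn out to have HBV are exposed to the risk. More doses can precede the result in the no-methotrexate cohort, because its schedule is front-loaded. That cohort also receives patients kept off methotrexate by abnormal liver tests.

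**Working it through.** **Step 1. Do other provisions close the gap?**

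- The 72-hour window and the Serology mark in Appendix 3 fix when blood is drawn. Neither says when the result is due.
- The ALT/AST and bilirubin limits in 3.1.1.2 bar only the methotrexate regimen. Patients above them go to section 3.6, where dose-dense rituximab is the default.
- The exclusion of Child-Pugh class B or C (2.1.2.6) and the investigator's discretion over undue risk (2.1.2.9) do not depend on HBV serology.
- HAART may happen to contain an HBV-active drug. The protocol neither requires that nor requires HAART before dose 1. The tenofovir-free advice discourages one of the two agents that 3.9.6 names, but leaves lamivudine and others available.
- Appendix 9 has staff settle the HAART regimen at admission, but its admission list has no HBV item.
- Liver tests are scheduled during treatment: a hepatic panel on Day 1 of each cycle and every other day until methotrexate clears (3.8.3), and clinical labs on every dose-dense dosing day (Appendix 3). These would detect reactivation, not prevent it.

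The gap is narrowed, not closed.

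**Step 2. How many doses could precede the result?**

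The plan states no figure to reproduce. The inputs from the protocol are the dosing days: 1, 3, 5, 8, 15 and 21 in the dose-dense cohort, and every 14 days from Day 1 for six doses in the main cohort. The lead L, from blood draw to Day 1, is taken as 0 to 3 days, following the 72-hour window. Turnaround T is an assumption of 1 to 10 days.

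- Result day = 1 − L + T
- Doses before the result = number of dosing days earlier than the result day
- Wait if the result is required first = max(0, T − L)

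Example: T = 10 and L = 0 give result day 1 − 0 + 10 = 11. The dose-dense doses on Days 1, 3, 5 and 8 fall earlier, so the count is 4. With L = 3 the result day is 8, and the doses on Days 1, 3 and 5 fall earlier, so the count is 3.

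| T (days) | Dose-dense doses before result, L = 0 / L = 3 | Main-cohort doses, L = 0 / L = 3 | Wait in days if result required, L = 0 / L = 3 |
|---|---|---|---|
| 1 | 1 / 0 | 1 / 0 | 1 / 0 |
| 3 | 2 / 0 | 1 / 0 | 3 / 0 |
| 5 | 3 / 1 | 1 / 1 | 5 / 2 |
| 7 | 3 / 2 | 1 / 1 | 7 / 4 |
| 10 | 4 / 3 | 1 / 1 | 10 / 7 |

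Over the whole range, 0 to 4 of 6 dose-dense doses and 0 to 1 of 6 main-cohort doses precede the result, and the wait is 0 to 10 days. Benefit and cost move together: the case with four early doses is also the case with a ten-day wait. If the lead is at least as long as the turnaround, both are zero. With L = 10, that holds for every T up to 10.

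**The case against.** The strongest reply is that the two sections do not contradict each other. A reader might infer that 3.9.6 requires cover before the first rituximab dose and that 3.8.2.1.7 breaches it. The text does not go that far. It sets cover for patients with serologic evidence of HBV without saying that cover must precede dose 1, and for anti-HB core alone it asks only that cover be considered. Patients with a documented positive result can be covered from the start, and others once the result returns. The waiver is explicit and has a plausible reason, since section 1.2.1 gives a pre-HAART median survival of 2 to 3 months. All of this stands. What remains is that cover begun after dose 1 does not span the first cycle, and the stated rule permits this for a drug the protocol itself flags.

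A reader might also infer that patients are likely to be harmed. The documents do not support that. They give no HBV prevalence, no turnaround and no measure of the protection lost by starting some days late. The counts above are doses, not harm, and the number of patients affected could be zero.

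Finally, section 2.2.1 allows viral studies at any time before entry, which might be read as already permitting an early hepatitis draw. Its list of studies does not name hepatitis serology, so an earlier draw needs a new permission. A long lead may also be hard to achieve in urgent disease.

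**Conclusion.** The point holds as a cheap patient-safety improvement. Section 3.8.2.1.7 permits rituximab before HBsAg and anti-HB core results are known, and nothing else in the protocol reliably covers the interval. It applies only to patients with undocumented HBV status and no HBV-active drug in their HAART at dose 1. The size of that group is unknown; section 6.1.3 caps the whole trial at 28 patients, with up to 10 in the no-methotrexate cohort.

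The dose counts rest on the assumed turnaround of 1 to 10 days. With a turnaround of 3 days or less and the full 72-hour lead, no dose precedes the result. In the main cohort the effect never exceeds one dose over the assumed range. The primary endpoint, sample size and analysis are not affected.

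**What to change.** 1. **Section 3.8.2.1.7.** Replace the general waiver with wording such as: *HBsAg and anti-HB core results are reviewed before the first rituximab dose; this blood may be drawn at screening. Results of the other hepatitis studies may follow the start of treatment.*
2. **Appendix 9, admission list.** Add a check that HBsAg and anti-HB core have been reviewed, next to the item on choosing the HAART regimen.
3. **Urgent cases.** If treatment cannot wait, rituximab may start. Before dose 1 the investigator documents a decision on whether to include an HBV-active agent until the result returns. Lamivudine is one option: 3.9.6 already names it and the tenofovir-free advice does not restrict it. This does not impose empiric cover on everyone. It adds a recorded decision to the discretion over HAART that already exists.

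No new test is needed, because the serology is already part of the baseline assessment. The downside is a wait equal to turnaround minus lead time, 0 to 10 days over the assumed range. An earlier draw shortens the wait, and the urgent route avoids it.
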